#### F. Allocation of interventions

- **a. Methods for randomisation and stratification.** PCCs in clinics randomized to Opioid Wizard (in 15 of the 30 clinics randomized in the parent study) will be randomized 1:1 to the stigma reduction or comparison training, stratified by clinic and waiver status. Randomization will be generated using SAS software.
- b. Methods for concealment of allocation. PCCs will be blind to their randomized MyLearning training assignment. The study statistician ([name]) will generate the randomization assignment, and a study team member will submit that list to HP MyLearning staff. Study team members capturing outcome data from surveys, Opioid Wizard, and Epic (including use rates, buprenorphine prescriptions) will also be blind to treatment assignment.

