# L. Sample size

There are 449 PCCs in the 30 clinics being considered for randomization to the parent study, COMPUTE 2.0, with an average of 15 per clinic (range 4-36). To the extent that the parent study will seek balance between treatment arms in clinic size, and by extension number of PCCs, we estimate that 225 PCCs will be in intervention clinics and eligible for this study. We have estimated power for PCC participation rates of 50%, 65%, and 80% with equal numbers of PCCs per arm. Approximately 93% of PCCs at HP are not waivered, which would reduce available sample sizes for H1b and H1c to 208 PCCs. The power analysis was calculated using G\*Power 3.1 and determined the minimal detectable standardized effect between groups for each outcome given available sample size,  $\alpha_2$  = .05, and desired power (see Table 1). Given these assumptions, we will have the ability to detect moderate differences (80% power: d = 0.42-0.55; RR=1.28-1.58) between the groups.

For Aim 2, the regression models will include PCCs in both arms and up to 4 covariates. Given sample size,  $\alpha_2$  = .05, and desired power, we will have adequate power to detect small effects for H2a (80% power:  $f^2$  = 0.05-0.08) and moderate effects for H2b (80% power: RR=1.29-1.60).

Table 1. Minimal detectable	Table 1. Minimal detectable standardized effects based on PCC						
participation rate and desired power.							
PCC participation= 50% 65% 80%							

	112 F	PCCs	146 F	PCCs	180 F	PCCs	
ро	wer =	0.80	0.90	0.80	0.90	0.80	0.90
H1a: OUD Stigma	d	0.49	0.57	0.47	0.54	0.42	0.49
H1b, H1c: Intentions	d	0.55	0.64	0.48	0.56	0.44	0.51
H1d: CDS Use: 30%	RR	1.58	1.69	1.50	1.59	1.44	1.52
50%	RR	1.44	1.51	1.38	1.44	1.34	1.39
70%	RR	1.36	1.43	1.31	1.37	1.28	1.33
H2a: Intentions	f 	0.08	0.10	0.06	0.08	0.05	0.06
H2b: CDS Use: 30%	RR	1.60	1.71	1.52	1.61	1.46	1.54
50%	RR	1.45	1.53	1.39	1.46	1.35	1.41
70%	RR	1.37	1.44	1.32	1.38	1.29	1.34
Note. Cohen's d = d; Co	hen's	$f^2 = f^2; I$	Rate ra	tio = RF	₹.		

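### The detectable rate ratios for H1d in Table 1 (RR 1.28-1.58 at 80% power) are not supported as a comparison of two arms on the inputs the plan states

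*Combined protocol and SAP*

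**What the plan says.** Section L reports that G*Power 3.1 was used to find the "minimal detectable standardized effect between groups for each outcome given available sample size", with two-sided alpha 0.05. It adds: "We have estimated power for PCC participation rates of 50%, 65%, and 80% with equal numbers of PCCs per arm". Out of an estimated 225 eligible clinicians, this gives N = 112, 146 and 180.

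For H1d, Table 1 lists rate ratios at base use of 30%, 50% and 70%. The text sums up the Aim 1 rows with "we will have the ability to detect moderate differences (80% power: d = 0.42-0.55; RR=1.28-1.58) between the groups". Section L does not name the regression routine, the distribution of the predictor or the exposure per clinician.

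Three other places bear on the point:
- Section F.a: clinicians "will be randomized 1:1 to the stigma reduction or comparison training". H1d in section C is an arm-against-arm hypothesis.
- Section H.b.iv: the outcome is one use proportion per clinician over six months of eligible visits.
- Section E.a: every randomized clinician enters the Wizard-use analysis, whether or not they complete the training. That is about 225, not 112 to 180.

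**The concern.** A rate ratio from a regression power routine means different things for different predictors. With a standard-normal predictor (variance 1) it is the effect of a one-SD shift. With a 1:1 arm indicator (variance 0.25) it is treatment against control. At the same sample size and exposure, the second needs a much larger ratio for the same power. If the H1d rows were run with the first setting, the figures do not answer the question that section L says they answer.

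H1d is the objective outcome among the primary ones, and section M makes the mediation analysis conditional on an H1d effect. A reader will use this power statement to judge how informative the H1d comparison can be.

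**Working it through.** **Inputs.** From section L: N = 112, 146, 180; base rates 0.30, 0.50, 0.70; two-sided alpha 0.05; power 0.80 and 0.90. From section F.a: 1:1 allocation. Assumed, because not stated: Poisson regression, Wald test, one exposure unit per clinician, no covariates.

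**Formula.** Power = Φ( ln(RR) × √(N × base × exposure × (1 − R²) / V) − 1.96 ), where
- standard-normal predictor: V = exp(−ln(RR)² / 2);
- 1:1 binary predictor: V = 2 + 2/RR.

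**Step 1: reproduce the plan's figures.** Take N = 112, base 0.30, RR 1.58 and a normal predictor. Then ln(RR) = 0.457, V = 0.901, N × base = 33.6, and 0.457 × √(33.6/0.901) = 2.79. Power is Φ(0.83) = 80%. Solving for exactly 80% gives 1.582. Across the table, 17 of the 18 H1d cells match to two decimals; the exception is 1.446, printed as 1.44. With R² = 0.05 the same formula matches all 18 H2b cells.

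**Step 2: change only the predictor to a 1:1 arm.** Same cell: expected events are 56 × 0.30 = 16.8 and 16.8 × 1.58 = 26.5. SE(ln RR) = √(1/16.8 + 1/26.5) = 0.312, z = 0.457/0.312 = 1.47, and power = Φ(1.47 − 1.96) = 31%. The 80% cells:

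| Base use | N | Printed RR | Normal predictor | 1:1 arm | Use implied by 1:1 arm RR | Power of 1:1 arm at printed RR |
|---|---|---|---|---|---|---|
| 30% | 112 | 1.58 | 1.582 | 2.27 | 68% | 31.1% |
| 30% | 146 | 1.50 | 1.501 | 2.07 | 62% | 31.2% |
| 30% | 180 | 1.44 | 1.446 | 1.94 | 58% | 30.7% |
| 50% | 112 | 1.44 | 1.437 | 1.92 | 96% | 31.6% |
| 50% | 146 | 1.38 | 1.377 | 1.79 | 89% | 31.6% |
| 50% | 180 | 1.34 | 1.335 | 1.69 | 85% | 31.8% |
| 70% | 112 | 1.36 | 1.362 | 1.75 | 123% | 30.9% |
| 70% | 146 | 1.31 | 1.313 | 1.64 | 115% | 30.6% |
| 70% | 180 | 1.28 | 1.279 | 1.57 | 110% | 31.1% |

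The 1:1 arm at unit exposure matches no printed H1d cell. At the printed 90% ratios it has 39.2-40.4% power. Simulating three of the 80% cells with score, Wald and likelihood-ratio tests gave 30-32%.

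**Step 3: use the H1d analysis set.** With N = 225 and unit exposure, power at the printed 80% ratios is 37-56% (for example 55% at RR 1.58 with base 30%, and 38% at RR 1.28 with base 70%).

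**Step 4: test the rival explanation.** Let exposure vary with a 1:1 arm. At 3.63 units per clinician, all 18 H1d cells match, and 17 of 18 H2b cells match with R² = 0.05. The reason is that the ratio of the two V terms barely changes over the table: 3.266/0.901 = 3.63 at RR 1.58 and 3.5625/0.970 = 3.67 at RR 1.28. The two settings are almost the same calculation.

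**The case against.** The strongest reply is that the normal-predictor setting is inferred and the numbers do not prove it. This stands. Over both blocks the normal predictor matches 17 + 18 = 35 cells and the binary arm at exposure 3.63 matches 18 + 17 = 35, so fit does not separate them. Nor is an exposure of that order absurd. Section D.b requires at least 50 eligible patients per clinic and section L gives 15 clinicians per clinic on average; 50/15 = 3.3, although that counts patients, not visits. What favours the normal predictor is that it needs no fitted value and suits the H2b stigma score, whereas 3.63 appears nowhere and the match fades quickly (13 of 18 H1d cells at 3.60). If 3.63 was in fact used, the whole H1d claim rests on an undisclosed input.

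The second reply is that each clinician has many visits, so power may be well above 31%. This also stands. In the binary model, power at the printed 80% ratios is 54-56% at exposure 2, 83-84% at 4 and 90-91% at 5. Comparing mean proportions, with power = Φ( base × (RR − 1) / (SD × √(4/N)) − 1.96 ), it is 84-99% at an assumed SD of 0.30 and 60-92% at 0.40. The plan gives neither SD nor visits per clinician.

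A reader might therefore infer that the trial has 31% power for H1d, or that a null result is bound to be misread. The documents support neither. The 31% belongs to the unit-exposure reconstruction, and a null result would be judged by its confidence interval.

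**Conclusion.** The point holds in a limited form. On the inputs the plan states, RR 1.28-1.58 is not supported as the 80%-power contrast between two arms. The simplest account of the cells is a per-SD effect of a continuous predictor; the alternative needs an unstated exposure near 3.63. Conditional on Poisson regression and unit exposure, a 1:1 arm has about 31% power at the printed 80% ratios and a detectable RR of 1.57-2.27; at N = 225 the power is 37-56%. True H1d power cannot be worked out from the documents.

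It might also seem that 1.57-2.27 should simply be printed in place of 1.28-1.58. That would be unsound: every 70% cell implies use above 100%, as does the cell for 50% base use, N = 112 and 90% power (2.10 × 50% = 105%), and both N and exposure would still be wrong for this outcome. The H2b rows are not affected by the predictor issue.

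**What to change.** - Recompute the H1d rows as a 1:1 arm comparison of clinician-level use proportions, with N set to all randomized clinicians (about 225), in line with section E.a.
- State the model, the predictor coding, the between-clinician SD and the number of eligible visits per clinician. Show the last two over a range, since the documents give neither.
- Replace the H1d cells and the RR range in the summary sentence with the results, bounded so that use in either arm cannot exceed 100%.
- Limit the claim of moderate detectable differences to H1a-H1c unless the recomputation supports it for H1d.

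The cost is one block of Table 1 and one sentence. The stated figures may become less favourable. The sample, the outcome and the analysis do not change.

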# M. Analysis Strategies

All variables will be examined using descriptive statistics and graphical methods to examine distributions, potential outliers, and analysis assumptions across and within study arms. The hypotheses predict that PCCs in the stigma reduction intervention will report less stigma of people with OUD and greater intentions to get waivered and prescribe buprenorphine (among non-waivered PCCs), and will use Opioid Wizard at a greater proportion of eligible encounters. A generalized linear model framework will be used to test the Aim 1 hypotheses, using appropriate error distributions and link functions to normalize outcomes. For H1a through H1c, the primary outcomes will be stigma (H1a) and intentions to get waivered (H1b) and to prescribe buprenorphine (H1c), assessed immediately following the training; as a secondary outcome, we will examine whether the intervention has enduring effects on stigma and intentions by examining differences assessed at the 3-month follow-up survey. Secondary analyses will include an interaction term between intervention arm and waiver status to assess treatment heterogeneity.

In Aim 2, multiple linear regression models, controlling for PCC characteristics (i.e., age, gender, PCC type [physician, nurse practitioner, physician assistant], and waiver status [H2b only]) will be used to examine whether self-reported OUD stigma is related to (1) intention to get waivered to prescribe buprenorphine and (2) Opioid Wizard use. Secondary analyses will include an interaction term between stigma and waiver status to examine whether waiver status moderates the association between stigma and Opioid Wizard use.

In secondary analysis, we will examine whether self-reported stigma mediates the effect of the intervention on Opioid Wizard use. If the intervention affects Opioid Wizard use (H1d), and stigma is related to Opioid Wizard use (H2b), we will use a product of coefficients approach to quantify how much of the intervention effect is mediated by stigma. In other exploratory analyses, we will examine whether PCCs in the stigma reduction arm prescribe MOUD and /or naloxone to eligible patients at a higher rate than PCCs in the comparison arm, controlling for pre-Opioid Wizard prescribing behavior. We will also examine whether PCCs in the stigma reduction arm prescribe opioids to eligible patients at a lower rate than PCCs in the comparison arm, controlling for pre-Opioid Wizard prescribing behavior. Further, as a follow-up to H1b, we will examine whether PCCs in the stigma reduction arm are more likely to get waivered than control PCCs using a logistic regression framework. To understand how PCC experience with patients at high risk for problems with opioids may have influenced their decision to participate in this study, we will compare PCC prescribing and referral behaviors among PCCs who completed the training to those who did not among all randomized PCCs.

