# C. Objectives, Aims, & Hypotheses

In response to NOT-OD-101: HEAL Initiative: Notice of Special Interest (NOSI) regarding the Availability of Administrative Supplements to Support Strategies to Reduce Stigma in Pain Management and OUD and Treatment, this project will evaluate an intervention to reduce stigma in PCCs by integrating stigma reduction training into the Opioid Wizard training. PCCs will be randomized to this novel stigma reduction training, grounded in stigma science, or an attention-control training. The overall goal of this project is to determine whether stigma reduction training reduces PCC stigma, increases intention to get waivered to prescribe buprenorphine or to prescribe buprenorphine if a waiver were no longer required, and ultimately increases the likelihood that PCCs use Opioid Wizard.

Aim 1: To examine whether a PCC training to reduce stigma toward people with OUD, compared to an attention-control training, reduces stigma, increases intention to get waivered, increases intention to prescribe buprenorphine if a waiver were no longer required, and increases the likelihood of using Opioid Wizard.

**H1a:** PCCs who are randomized to stigma reduction training will report less stigma towards patients with OUD compared to PCCs who are randomized to control training.

**H1b:** Among non-waivered PCCs, PCCs who are randomized to stigma reduction training will report greater intention to get waivered to prescribe buprenorphine than PCCs who are randomized to control training.

**H1c:** Among non-waivered PCCs, PCCs who are randomized to stigma reduction training will report greater intention to prescribe buprenorphine for OUD in the next year if a waiver were no longer required than PCCs who are randomized to control training.

**H1d:** PCCs who are randomized to stigma reduction training will use Opioid Wizard at a greater proportion of visits where the PCC is alerted to high risk than PCCs who are randomized to control training.

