# Aim 2: Examine the relationship between PCC stigma and intention to get waivered, and likelihood of using Opioid Wizard.

**H2a:** Among non-waivered PCCs, PCCs who report lower stigma will report greater intention to get waivered to prescribe buprenorphine.

**H2b:** PCCs who report lower stigma will be more likely to use Opioid Wizard at flagged visits.

As secondary outcomes, we will gather additional objective measures of PCC behavior, including PCC prescribing and referral behavior and new waivers among previously non-waivered PCCs. In secondary analyses, we will examine if waiver status at the time of the intervention moderates the impact of the intervention on stigma attitudes and use of Opioid Wizard. Additionally, in exploratory analysis, we will examine whether stigma mediates the effect of the intervention on Opioid Wizard use and if receiving the stigma and/or control intervention increases the number of PCCs getting waivered or the number of patients receiving treatment (prescriptions or referrals for treatment). Results of this work will inform future interventions aimed at reducing stigma among PCCs for OUD and a variety of other stigmatized health conditions, including other SUDs.

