# I. Post-recruitment retention strategies

- a. Participant retention. To encourage PCCs to complete the training, they will receive up to 4 reminders and will be offered a \$100 incentive. We may also ask clinic leaders to remind PCCs to complete training. Further, PCCs will be offered an additional \$25 incentive for completing the follow-up assessment at 3 months. Direct email communications will be sent to request and remind them about the survey. There may be volunteer bias in those who complete the training; however, this should not compromise internal validity as factors that predict participation should be random across intervention assignment. We will describe differences between completers and non-completers (e.g., gender, PCC type, waiver status, clinic).
- **b. Participant withdrawal.** Participants may withdraw from the study at any time. It is possible that they will not complete the training or the surveys. However, the training and surveys are designed to be short so they do not overburden participants.

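### Randomization is stratified by clinic, but section M names no clinic term for the Aim 1 models; leaving it out keeps H1a-H1c valid and forgoes about 0 to 3 points of power at an assumed ICC of 0 to 0.10

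*Combined protocol and SAP*

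**What the plan says.** Section F (a) states that PCCs "will be randomized 1:1 to the stigma reduction or comparison training, stratified by clinic and waiver status". Section M then gives the Aim 1 method in one sentence: "A generalized linear model framework will be used to test the Aim 1 hypotheses, using appropriate error distributions and link functions to normalize outcomes". No covariate, clinic term or random effect is named for the main models.

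Elsewhere:

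- **Aim 2 models (section M):** the covariates are age, gender, clinician type and, for H2b, waiver status. Clinic is not among them.
- **Waiver status in Aim 1:** it enters only through a secondary arm-by-waiver interaction. Section C describes this as follows: "we will examine if waiver status at the time of the intervention moderates the impact of the intervention on stigma attitudes".
- **3-month survey (section M):** a secondary analysis looks for "enduring effects on stigma and intentions by examining differences assessed at the 3-month follow-up survey". It too names no clinic term.
- **H1b and H1c (section C):** both are restricted to PCCs without a waiver, so waiver status is constant in those models.
- **Clinic (section I):** it appears as one of the characteristics on which completers and non-completers will be described.

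**The concern.** When randomization is stratified by a factor that predicts the outcome, the arms are balanced on that factor and the true variance of the arm difference is reduced. A model without the factor still charges its variance to the error term, so the standard error is too large and the test conservative. This is not the cluster-randomized problem, in which ignoring clinic makes the standard error too small. Here both arms occur within every clinic, and the direction is the opposite.

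What is at stake is a little power. The pool of about 225 PCCs is fixed by the parent trial, and section L allows for participation as low as 50%, so precision cannot easily be bought by recruiting more. Naming the term in advance also removes a later choice between no clinic term, a random intercept and fixed effects, which do not perform alike at these sample sizes.

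**Working it through.** **Inputs from the documents.** There are 15 intervention clinics (section E) and 225 eligible PCCs, with a mean of 15 per clinic and a range of 4 to 36 across the 30 parent-trial clinics (section L). Participation of 50%, 65% and 80% gives N = 112, 146 and 180. With 208 non-waivered PCCs, N for H1b and H1c is 104, 135 and 166. Alpha is 0.05, read as two-sided.

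**Assumed.** ICC of 0, 0.05 and 0.10, with 0.20 as an outer value, because the documents give none.

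**Step 1: reproduce Table 1 at 80% power.** For an unadjusted two-sample t-test with equal arms, the noncentrality is d × √N / 2. Solving for d:

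| Hypothesis | N | d recomputed | Table 1 |
|---|---|---|---|
| H1a | 146 | 0.467 | 0.47 |
| H1a | 180 | 0.420 | 0.42 |
| H1b, H1c | 104 | 0.555 | 0.55 |
| H1b, H1c | 135 | 0.486 | 0.48 |
| H1b, H1c | 166 | 0.437 | 0.44 |

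These agree to within rounding, so the planned power assumes no clinic term. The H1a cell at N = 112 does not reproduce: the calculation gives 0.534 against the printed 0.49, and power at 0.49 is about 73%. That is a separate matter; 0.534 is used below.

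**Step 2: formula.** With total SD 1 and responders balanced within clinic, the true variance of the arm difference is about (1 − ICC) × 4/N, while the unadjusted model estimates 4/N. With critical value c and noncentrality λ:

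- unadjusted power = Φ((λ − c)/√(1 − ICC))
- adjusted power ≈ Φ(λ/√(1 − ICC) − c)
- unadjusted type I error = 2 × (1 − Φ(c/√(1 − ICC)))

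For N = 180, d = 0.42, ICC = 0.10: λ = 0.42 × √180 / 2 = 2.82, c = 1.973 and √0.9 = 0.949. Unadjusted power is Φ(0.89) = 81.3%. Adjusted power is about Φ(1.00) = 84%. Type I error without clinic is 3.75%. Across the H1a-H1c sample sizes the gain is about −0.2 to −0.1 points at ICC 0, 1.2 to 1.3 at 0.05 and 2.5 to 2.7 at 0.10.

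**Step 3: simulation.** Participation comes after randomization, so balance among responders is imperfect. The simulation used:

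- 20,000 runs per setting (Monte Carlo error about 0.3 points for power and 0.15 for type I error), with models compared on the same data
- clinic sizes from 4 to 36, one waivered PCC per clinic and an assumed waiver effect of 0.5 SD
- 1:1 allocation within clinic-by-waiver strata, with independent random participation
- a t-test, against a REML random-intercept model with a t reference on within-clinic degrees of freedom

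H1a power (%), unadjusted → clinic random intercept:

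| Participation | ICC 0 | 0.05 | 0.10 | 0.20 |
|---|---|---|---|---|
| 50% | 78.9 → 79.0 | 79.8 → 80.8 | 80.2 → 82.1 | 81.1 → 85.7 |
| 65% | 79.2 → 79.5 | 79.9 → 81.0 | 80.5 → 82.7 | 80.9 → 86.3 |
| 80% | 78.9 → 79.2 | 79.7 → 80.8 | 80.5 → 82.9 | 81.5 → 86.8 |

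The unadjusted values at ICC 0 fall just below 80% because the assumed waiver effect adds outcome variance. Other results at ICC 0, 0.05 and 0.10:

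- **H1b, H1c:** gains of 0.2-0.3, 0.9-1.2 and 2.1-2.6 points. With outcomes cut to five categories the gains are 0.1-0.2, 0.8-1.0 and 1.6-1.9.
- **3-month survey (70% response assumed):** gains of 0.1-0.3, 0.9-1.2 and 1.6-1.9 points for H1a-H1c.
- **Type I error:** unadjusted 4.9-5.3%, 4.5-4.8% and 4.2-4.5%. With the random intercept it is 4.9-5.5%.
- **Equal clinics of 15 (H1a, 50%):** gains of 0.2, 1.1 and 2.2 points, so the assumed spread of clinic sizes matters little.

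A second simulation (8,000 runs per setting) gave random-intercept gains of 0, 0.8-1.6 and 2.1-2.6 points.

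**Step 4: fixed clinic effects.** Fourteen fixed effects lose power when the ICC is small. At 50% participation, H1a goes from 78.9 to 75.6% (ICC 0) and from 79.8 to 78.2% (ICC 0.05). At 3 months with about 79 responders, it goes from 78.4 to 72.2% and from 78.9 to 74.5%.

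**Step 5: waiver status.** With ICC 0 and waiver effects of 0, 0.5 and 1.0 SD, the ratio of the mean unadjusted standard error to the true SD of the estimate was 0.990-1.006 with one waivered PCC per clinic. Stratifying on waiver status therefore makes no difference to the standard error. Adding it to H1a as an ordinary covariate gains 0.1 to 0.6 points under the 0.5 SD assumption.

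**The case against.** The strongest reply is that nothing here is an error. A generalized linear model framework does not exclude a clinic term, and the default of omitting it harms nothing. The size rests on an ICC that the documents do not give, and nothing in them shows that stigma or intentions cluster by clinic within one health system. Between ICC 0 and 0.02 the formula gives at most 0.5 points. All of this stands, and it is why the point is optional and conditional.

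A second reply is that the remedy is not free. A random intercept turns the model into a mixed model, needs a degrees-of-freedom rule and, under a non-identity link, can change what the arm coefficient estimates. Its simulated type I error reached 5.5%, so part of the small gain may come from a test marginally above nominal. This stands as a reason to write the term down exactly. The power figures apply to a linear model with an identity link.

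A third reply is that waiver status adds little in H1a: about 7% of PCCs hold a waiver, and the 0.5 SD effect is assumed. That is correct. The case for including it is that it was a randomization factor and costs one coefficient.

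Finally, some inputs are approximate. The 4-36 range describes all 30 parent clinics, and section L implies 225 − 208 = 17 waivered PCCs where the simulation used 15. The equal-clinic run suggests that the first hardly matters, and two PCCs in 225 would not change the conclusion about clinic.

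**Conclusion.** The concern holds as an optional improvement. Section M names no clinic term for Aim 1 although clinic is a randomization stratum. If clinic is left out, the H1a-H1c tests are valid and slightly conservative, and they forgo about 0 to 3 points of power over an assumed ICC of 0 to 0.10 (about 1 point at 0.05). The larger gains of 4 to 5 points need an ICC of 0.20 and should not be relied on.

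The omission causes no bias, no inflation of type I error, and no shortfall against the Table 1 cells that reproduce. The conclusion assumes a roughly Normal outcome analysed on its own scale, participation unrelated to arm, and a random intercept as the alternative. It says nothing about H1d, which was not simulated, or about selection into the survey.

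**What to change.** Add one sentence to section M: the H1a-H1c models, at both the immediate and the 3-month survey, include clinic as a random intercept, and H1a also includes waiver status as recorded at randomization. The recorded value matters because section H collects waiver status in a survey after training and section K extracts it at the end of follow-up; neither is the stratification value. H1b and H1c need clinic only.

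The same sentence should state the link and the degrees-of-freedom rule; the figures above used an identity link and a t reference on within-clinic degrees of freedom. It should not specify 14 fixed clinic effects, which would cost power at the lower participation rates if clinics are similar.

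The cost is one variance component in each of H1a-H1c and one further coefficient in H1a. No new data are needed, since both factors were used for allocation and so exist for every randomized PCC.
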